7.2 Statistical Methods

Statistical Methods

All statistical analyses will be carried out using SAS software, version 9.4. The level of significance will be set at $\alpha = .05$ (two-tailed) and, to address multiple testing (where applicable), p-values will be adjusted using the False Discovery Rate.

Primary Aim

Data Analysis Plan for Primary Aim 1 (Hypotheses 1a–1d)

Primary Continuous Outcome: CDRS-R Total Score

Depression severity (measured by CDRS-R total) over the 6-week study period will be the primary continuous outcome measure. A linear mixed model analysis of repeated measures will be used to evaluate the rTMS Treatment (low frequency 1 Hz rTMS vs. high frequency 10 Hz rTMS) by biomarker status (high baseline ICF vs. low baseline ICF) interaction effect on depression severity (CDRS-R total) over 6 weeks of rTMS in depressed adolescents. The model will contain fixed effects terms for rTMS treatment, biomarker status, time, rTMS treatment \times biomarker status interaction, and baseline CDRS-R total score as a covariate. We will consider the inclusion of pubertal state and treatment resistance (as defined by Antidepressant Treatment History Form [ATHF] score) during the study period as additional covariates in the mixed model. Restricted maximum likelihood estimation, Type 3 tests of fixed effects, and generalized least squares will be used, with the Kenward-Roger correction applied to the appropriate and best fitting covariance structure. The sandwich (robust covariance matrix) estimator will also be considered. Least squares (LS) means will be estimated as part of the mixed model. Tests of Simple Effects will be examined so as to partition the interaction LS means effects; i.e., simple group main effects of biomarker status at each level of rTMS treatment (Hypotheses 1a, 1b) and simple group main effects of rTMS treatment at each level of biomarker status (Hypotheses 1c, 1d) will be examined. Cohen's *d* and Hedges' *g* will be calculated and interpreted as the effect size estimator for the between-Participants group main effects. A separate linear mixed model repeated measures analysis similar to that described above will also be implemented over 6 weeks of acute rTMS treatment and throughout the 6-month follow-up period. The PROC

MIXED procedures (mixed model approach) in SAS software will make use of all available data from all participants from the efficacy analysis set, and provide a robust mechanism for handling data that are assumed missing at random (see sensitivity analysis section below for MNAR).

Secondary Aim

Data Analysis Plan for Secondary Aim 2 (Hypotheses 2a–2d)

Secondary Continuous Outcome: Intracortical Facilitation (ICF)

Intracortical Facilitation over the 6-week study period will be the secondary continuous outcome measure. A within-Participants linear mixed model analysis of repeated measures will be used to examine the change in ICF over 6 weeks of rTMS treatment in depressed adolescents. We will consider the inclusion of pubertal state and treatment resistance (as defined by ATHF score) during the study period as a covariate in the mixed model. A mixed model analysis will be conducted on ICF for those who receive 6 weeks of low frequency (1 Hz) rTMS treatment (Hypothesis 2a) and, in a separate model, for those who receive 6 weeks of high frequency (10 Hz) rTMS treatment (Hypothesis 2c). Restricted maximum likelihood estimation, Type 3 tests of fixed effects, and generalized least squares (LS) will be used, with the Kenward-Roger correction applied to the appropriate and best fitting covariance structure. The sandwich (robust covariance matrix) estimator will also be considered. LS mean contrasts (between ICF measurement time periods) from the mixed model will also be examined. A separate linear mixed model analysis similar to that described above will also be implemented over 6 weeks of acute rTMS treatment and throughout the 6-month follow-up period. A nonlinear mixed model will be considered (e.g., exponential decay/growth model) to estimate ICF over the 6 weeks of rTMS treatment (if the pattern of ICF values suggests that a nonlinear model is deemed necessary).

A linear mixed model repeated measures analysis similar to that described above will also be used to examine the relationship between measures of ICF (as the response variable) and depressive symptoms (CDRS-R total as a time-varying covariate) over the 6 weeks of rTMS treatment. We will consider the inclusion of pubertal state and treatment resistance (as defined by ATHF) during the study period as a covariate in the mixed model. The parameter estimates (regression coefficients) will be interpreted from the solution for fixed effects in the mixed model analysis for those who receive 6 weeks of low frequency (1 Hz) rTMS treatment (Hypothesis 2b) and for those who receive 6 weeks of high frequency (10 Hz) rTMS treatment (Hypothesis 2d). A separate linear mixed model analysis similar to that described above will also be implemented over 6 weeks of acute rTMS treatment and throughout the 6-month follow-up period. A nonlinear mixed model will be considered to estimate ICF over the 6 weeks of rTMS treatment from CDRS-R total (if the pattern of ICF and CDRS-R total suggests that a nonlinear model is deemed necessary).

Data Analysis Plan for Exploratory Aim 3 (MRI/MRS)

A within-participants linear mixed model analysis of repeated measures will be used to examine baseline differences between depressed adolescents and healthy control adolescents (Hypotheses 1 and 2); and the change in cortical MRS measures of GABA and Gln/Glu over 6 weeks of rTMS treatment in depressed adolescents. Separate mixed models will be conducted on cortical GABA and Gln/Glu for those who receive 6 weeks of low frequency (1 Hz) rTMS treatment

(Hypotheses 3 and 4) and for those who receive 6 weeks of high frequency (10 Hz) rTMS treatment (Hypotheses 5 and 6). A nonlinear mixed model will be considered (if the pattern of GABA and Gln/Glu values suggests that a nonlinear model is deemed necessary).

Data Analysis Plan for Exploratory Aim4

Moderator Effects of Anhedonia and Adversity on Treatment Outcome of Depression Severity

The multiple mediation/moderation path analytic model, as described in Preacher and Hayes will be used to estimate the direct effect as well as the total and specific indirect effects of rTMS treatment on depression severity (at the 6-week endpoint) through each of the potential baseline moderators (anhedonia and adversity) operating in parallel and, via a separate model, in serial, while controlling for any potential demographics/patient characteristics (not designated as mediators/moderators), including pubertal state and treatment resistance (as defined by ATHF score). A test of the indirect effects will be conducted by bootstrapping standard errors and confidence intervals (95% bias-corrected) from 5,000 bootstrap samples. The procedures of the PROCESS computational SAS macro developed by Hayes will be used to implement the path analytic-based multiple mediation/moderation model.

Sensitivity Analysis

In this section we present a brief sensitivity analysis plan to address incomplete response patterns according to a missing not at random mechanism. First, we will follow the outcome-based model framework of for longitudinal data with non-random missingness along with a model-based approach proposed for modeling both the treatment response and the missing data process.⁹⁰ That is, if deemed necessary, we will build longitudinal models for the data which includes a model for the dropout (or missing data) process so as to assess the sensitivity of the results about the dependence between dropout (or missingness) and treatment response. Additionally, if deemed necessary, we will consider implementing the semi-parametric shared parameter model approach as described in Tsonaka et al. (2009) to handle nonmonotonic nonignorable missingness for mixed-effects models. A Pattern-Mixture Model will also be considered (if necessary).⁹⁰ The results from such (non-random dropout/missingness) models will then be compared with the results of the proposed standard methods (dropout or missing at random models) so as to assess the sensitivity of the results to the effect of dropouts (or incomplete response patterns according to a missing not at random mechanism).

8 Safety and Adverse Events

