2.1 Primary Objective

Aim 1 examines the relative efficacy of 6 weeks low frequency (1 Hz) or high frequency (10 Hz) left prefrontal rTMS according to a baseline ICF (**ICF-15 % MEP amp**) measure of glutamatergic tone in depressed adolescents. We will employ a biomarker stratified design. Depressed adolescents will be stratified by baseline ICF low (≤ 1.5) or ICF high (>1.5) groups prior to randomization.

- We expect that 6 weeks of 1 Hz rTMS will have greater efficacy (assessed by improvement in CDRS-R) in depressed adolescents with high baseline ICF compared to adolescents with low baseline ICF.
- We expect that 6 weeks of 10 Hz rTMS will have greater efficacy (assessed by improvement in CDRS-R) in depressed adolescents with low baseline ICF compared to adolescents with high baseline ICF.
- 6 weeks of 1 Hz rTMS will have greater efficacy (assessed by improvement in CDRS-R) than 6 weeks of 10 Hz rTMS in depressed adolescents with high baseline ICF.
- 6 weeks of 10 Hz rTMS will have greater efficacy (assessed by improvement in CDRS-R) than 6 weeks of 1 Hz rTMS in adolescents with low baseline ICF.

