[figure not shown]
To our knowledge the NeuroStar® TMS Therapy System in XPLORE research configuration has been used most often in prior investigational studies of adolescent depression.^{33,69} Our group has existing and ongoing collaborations with Neuronetics as documented in referenced IDE applications: G060269, G110091, G120121. The present, proposed IDE application would deliver investigational, therapeutic TMS therapy (1 Hz, 10 Hz, cTBS, and iTBS) with the NeuroStar® TMS Therapy System in XPLORE research configuration.

Although the interventional component of the study (randomized biomarker stratified trial of 1 Hz or 10 Hz rTMS and extension trial of cTBS or iTBS) is considered more than minimal risk to adolescents, TMS treatments offer a potential direct benefit for the individual participants.^{33,47} Notably all depressed, adolescent participants will receive an active form of TMS. There is no placebo or sham condition. In addition, the schedule of mood assessments and daily assessments during the interventional portion of the study for any adverse events has been developed for the purpose of monitoring the participants' well-being.

All families and participants for this study will be provided with a consent/assent form describing this study and providing sufficient information for Participants to make an informed decision about their participation in this study. This consent/assent form will be submitted with the protocol for review and approval by the Mayo Clinic IRB. The formal consent/assent of a participant, using the approved IRB consent/assent form, must be obtained before that participant undergoes any study procedure. This form must be signed and dated by the participant the participant's legally-authorized representative, and the individual obtaining informed consent/assent.

3 Study Design

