5.2 Method for Assigning Participants to Treatment Groups

Each participant will be assigned a unique identification upon signing the informed consent and assent form. This number will consist of an assigned 3-digit identifier. Participants will be identified by their assigned number and initials on the CRFs and source documents. The PI/Study Sponsor will maintain a master list linking Participant names and the identifying information indicated above

A Phase I randomization schedule will be generated by [name] (Study biostatistician). Participants will not be randomized until all entry (inclusion and exclusion) criteria have been met and all pre-study procedures have been satisfactorily completed. After stratification based on ICF biomarker status, eligible participants will be randomly assigned to receive one of the two treatment regimens (1 Hz or 10 Hz rTMS), and the next available randomization number for the participant's stratum will be recorded in the screening log and on the participant's CRF. Randomization numbers may not be reassigned. A permuted-block procedure will be used to randomly assign the treatment conditions, with a fixed block size for each stratum. Phase II is a trial of cTBS or iTBS for Phase I participants who did not have an adequate clinical response in Phase I. Participants will be assigned to 2 weeks of cTBS if their intracortical facilitation measure is >1.5 (building on the current speculation that cTBS would be expected to decrease cortical excitability and ICF measures). Participants will be assigned to 2 weeks of iTBS if their ICF (baseline assessment for TBS extension trial) is ≤ 1.5 .

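### Primary hypotheses 1a and 1b are tested as non-randomised ICF comparisons within one arm, with no condition on the interaction, so a purely prognostic ICF effect could be reported as differential efficacy for one of them

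*Combined protocol and SAP*

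**What the plan says.** Section 2.1 lists four expectations under Aim 1, and Section 7.2 refers to them as Hypotheses 1a to 1d. The first says that 1 Hz will have "greater efficacy (assessed by improvement in CDRS-R) in depressed adolescents with high baseline ICF compared to adolescents with low baseline ICF". The second is its mirror image: "6 weeks of 10 Hz rTMS will have greater efficacy (assessed by improvement in CDRS-R) in depressed adolescents with low baseline ICF", relative to those with high ICF. The third and fourth compare the two frequencies within the high and the low ICF group.

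The Study Summary and Section 7.2 both name the treatment-by-ICF interaction as the effect that the mixed model evaluates. Section 7.2 continues: "Tests of Simple Effects will be examined so as to partition the interaction LS means effects". It then assigns a test to each pair of hypotheses. The first pair is tested through "simple group main effects of biomarker status at each level of rTMS treatment (Hypotheses 1a, 1b". The second pair is tested by comparing the two frequencies inside each ICF stratum, which the plan words as "simple group main effects of rTMS treatment at each level of biomarker status (Hypotheses 1c, 1d". No sentence makes any of the four depend on a significant interaction or ranks 1c and 1d above 1a and 1b.

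On design, Section 5.2 states: "After stratification based on ICF biomarker status, eligible participants will be randomly assigned to receive one of the two treatment regimens". Section 2.2 states: "There is no placebo or sham condition". The primary model adjusts for baseline CDRS-R, while pubertal state and treatment resistance are only candidate covariates. Section 7.2 applies a False Discovery Rate adjustment where applicable but does not define the family of tests.

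**The concern.** Hypotheses 1a and 1b are worded as statements about efficacy, but the contrast assigned to them compares two groups that were not formed by randomisation and that all received the same active treatment. Without a sham arm, a difference in CDRS-R between high and low ICF within the 1 Hz arm may reflect response to 1 Hz. It may equally reflect a different natural course, or some other characteristic that goes with ICF. The contrast cannot tell these apart.

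The protocol gives reasons to think that ICF could be prognostic. Sections 1.1 and 1.5.1 say that anhedonia and adversity go with poor outcomes and may be linked to glutamatergic and GABAergic imbalance. Section 1.1 adds that this tone changes during development. Anhedonia and adversity are not covariates in the primary model.

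A primary hypothesis worded as efficacy could therefore be reported as supported when ICF has nothing to do with which frequency works better. The plan does not say how to read a significant 1a or 1b beside a non-significant interaction.

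**Working it through.** **Inputs from Section 7.1:** 25 per cell (four cells, 100 evaluable), two-sided alpha 0.05, 80% power, d = 0.61, 6 repeated measures, compound symmetry, correlation 0.50. **Assumption:** a prognostic ICF difference g in single-visit SD units, remaining after the model's covariates and identical in both arms. The documents give no value, so g runs from 0.2 to 0.61.

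**1. The plan's own figure.** The SD of a six-visit mean is sqrt((1 + 5 × 0.50)/6) = sqrt(0.583) = 0.764. The standard error of a 25 versus 25 contrast is 0.764 × sqrt(2/25) = 0.216. Power at 0.61 is Φ(0.61/0.216 − 1.96) = 80.6%, and the required n is 25 per group. The stated figures are thus those of one simple-effect comparison.

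**2. What a purely prognostic effect does to each contrast.** Let mean improvement be g in both high-ICF cells and 0 in both low-ICF cells, and write each contrast so that the predicted direction is positive.

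- 1a (1 Hz, high minus low): g − 0 = +g
- 1b (10 Hz, low minus high): 0 − g = −g
- 1c (high ICF, 1 Hz minus 10 Hz): g − g = 0
- 1d (low ICF, 10 Hz minus 1 Hz): 0 − 0 = 0
- Interaction: (g − 0) − (g − 0) = 0

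If low ICF has the better prognosis, 1a and 1b swap roles.

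**3. Size.** The normal approximation for 1a is Φ(g/0.216 − 1.96), which gives 15%, 28%, 46% and 64% at g = 0.2, 0.3, 0.4 and 0.5. A simulation of four cells of 25 (400,000 runs, t tests with 96 df) gives the rates below. Supported means significant in the predicted direction. BH is Benjamini-Hochberg over 1a to 1d, which is an assumed family.

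| g (SD) | 1a or 1b supported, unadjusted | 1a or 1b supported, BH | 1b significantly reversed, unadjusted | Interaction rejects | 1a or 1b (unadjusted) supported and interaction significant as predicted |
|---|---|---|---|---|---|
| 0 | 5.0% | 1.6% | 2.5% | 5.0% | 1.7% |
| 0.2 | 15.0% | 6.4% | 14.8% | 5.0% | 2.1% |
| 0.3 | 27.9% | 14.4% | 27.9% | 5.0% | 2.4% |
| 0.4 | 45.0% | 28.4% | 45.0% | 5.0% | 2.4% |
| 0.5 | 62.9% | 46.9% | 62.9% | 5.1% | 2.5% |
| 0.61 | 79.8% | 68.0% | 79.8% | 5.0% | 2.5% |

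Hypotheses 1c and 1d are each supported in 2.5% of trials at every g. Both 1a and 1b are supported in under 0.1%.

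**4. Power of the interaction.** Its standard error is 0.764 × sqrt(4/25) = 0.306. Power is Φ(0.61/0.306 − 1.96) = 51% for a difference-in-differences of 0.61 SD. For a full crossover of +0.61 and −0.61, which is a contrast of 1.22 SD, it is 98%. The contrast detectable with 80% power is (1.96 + 0.84) × 0.306 = 0.86 SD.

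**The case against.** The strongest reply is that the protection is already in the plan. The interaction is the named effect of the primary model, the simple effects are said to partition it, and the randomised contrasts 1c and 1d are specified. That is true and limits the point. What is missing is a rule that links 1a and 1b to the interaction. Partitioning suggests a follow-up test, but no condition is written.

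A reader might infer that a prognostic effect could confirm two of the four primary hypotheses at once. It could not. Hypotheses 1a and 1b predict opposite directions, so an effect equal in both arms supports one and reverses the other, and the crossover pattern does not appear. Nor is Aim 1 as a whole undermined, since the interaction, 1c and 1d keep their nominal error rates.

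A reader might also take the unadjusted rates as the plan's error rates. Section 7.2 provides for False Discovery Rate adjustment, which lowers them. It does not cure the problem, because under a prognostic effect one within-arm difference is real and the error lies in calling it efficacy.

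Regression to the mean is not a strong part of the case. The groups are split on ICF rather than CDRS-R, the same CDRS-R entry threshold applies to both, and baseline CDRS-R is in the model.

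Finally, no section says that a dosing claim would rest on 1a or 1b alone, and Section 7.1 describes the trial as a proof of concept. This stands, and it makes the point one of interpretation.

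**Conclusion.** The point holds for hypotheses 1a and 1b only. As written, the plan can report support for one efficacy hypothesis when ICF is purely prognostic. The unadjusted and Benjamini-Hochberg columns of the table give the size of the problem for each assumed g.

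These rates rest on the plan's design figures, on an even split into four cells of 25, and on prognostic effects that are assumed. The adjusted rates also assume a family of four tests. The documents do not show that ICF is prognostic for CDRS-R outcome, so the figures show how exposed the tests are and do not predict what will happen.

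The gap has practical weight because the interaction has only about 51% power for a difference-in-differences of 0.61 SD. A significant 1a or 1b beside a non-significant interaction is a realistic result.

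**What to change.** In Section 7.2, state that any conclusion that efficacy depends on ICF rests on the treatment-by-ICF interaction, followed by the randomised contrasts 1c and 1d. Then choose one of two treatments for 1a and 1b:

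- interpret them only after a significant interaction in the predicted direction, which holds false support to about 2.5% or less in the scenarios above; or
- report them as descriptive estimates with confidence intervals, worded as a difference in outcome by ICF within an arm.

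Define the False Discovery Rate family at the same time, and make the wording in Section 2.1 match.

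The change needs no new data and no change in sample size. Its cost is that 1a and 1b no longer stand alone as confirmatory, and that the ICF claim depends on an interaction test with good power for a full crossover (98%) but not for a contrast of 0.61 SD (51%). Reaching 80% power for that smaller contrast would need 50 per cell: 4 × (0.764 × 2.80/0.61)² = 49.2, rounded up.

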| 
Statistical Methodology
 | 
For the primary aim, a linear mixed model analysis of repeated measures will be used to evaluate the repetitive transcranial magnetic stimulation (rTMS) by biomarker status interaction effect on depression severity (CDRS-R score) over 6 weeks of rTMS.
 
For the secondary aim, a within-participant linear mixed model analysis of repeated measures will be used to examine the change in ICF over 6 weeks of rTMS.
 
For the exploratory aims, a within-subjects linear mixed model analysis of repeated measures will be used to examine the change in cortical MRS measures of GABA, glutamate, and glutamine over 6 weeks of rTMS treatment in depressed adolescents. A multiple mediation/moderation path analytic model will be used to estimate the direct effect as well as the total and specific indirect effects of rTMS treatment on depression severity (at the 6-week endpoint) through each potential baseline moderator (anhedonia and adversity).
 |

1 Introduction

This document is a protocol for a human research study. This study will be carried out in accordance with the procedures described in this protocol, applicable United States government regulations and Mayo Clinic policies and procedures.

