1.6 Anticipated Duration of the Clinical Investigation

It is anticipated that the proposed study will be five years in duration. For individual participants, Phase I (biomarker stratified, randomized trial of 1 Hz vs. 10 Hz rTMS) is 10 weeks in duration. Phase II (trial of cTBS vs iTBS based on ICF biomarker status) is 3 weeks in duration.

2 Study Objectives

The proposed study is a dose finding, effectiveness, and target validation study of rTMS for adolescent depression with a biomarker stratified design.⁷² Intracortical facilitation (ICF),⁶⁵ a transcranial magnetic stimulation (TMS) measure of cortical glutamatergic tone is the target engagement biomarker for the proposed trial. In phase I, a cohort of adolescents (ages 12-18) with clinically significant depression defined as 40 or greater on the Children's Depression Rating Scale-Revised (CDRS-R) will be stratified according to baseline ICF (high defined as > 1.5 or low defined ≤ 1.5) and then randomized to 6 weeks of either left prefrontal 1 Hz or 10 Hz rTMS. The research team will collect weekly ICF and CDRS-R measures during treatment. We will assess baseline anhedonia with a composite measure from relevant CDRS-R and Beck Depression Inventory-II (BDI-II) items. We will assess lifetime adversity with the Childhood Trauma Questionnaire (CTQ).

Participants in Phase I will be offered the opportunity to have 3 and 7 T MRI and MRS looking for biomarkers at baseline and after 6 weeks of treatment. A subgroup of depressed adolescent participants (up to 50) who do not respond to 1 Hz or 10 Hz rTMS will be offered the opportunity to participate in an exploratory, 2 week, trial of iTBS or cTBS based on ICF biomarker status (Phase II of the study). Participants with high baseline ICF (defined as > 1.5) will be assigned to cTBS treatment. Participants with low ICF (defined ≤ 1.5) will be assigned to iTBS.

7 T MRS measures Glutamate and GABA biomarkers in healthy adolescents and depressed adolescents. The overall goals are to examine cortical Glutamate and GABA neurochemical markers in adolescent depression and the impact of 1 Hz and 10 Hz rTMS on cortical glutamate and GABA neurochemical markers when compared to the healthy adolescent cohort.

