2.2 Secondary Objective

Aim 2 examines changes in weekly ICF and CDRS-R across 6 weeks of either 1 Hz or 10 Hz rTMS.

- We anticipate that ICF measures will decrease in depressed adolescents receiving 6 weeks of 1 Hz rTMS.
- We anticipate that ICF measures will increase in depressed adolescents receiving 6 weeks of 10 Hz rTMS.

Depressive symptom improvement will have a direct relationship with ICF decrease in depressed adolescents receiving 6 weeks of 1 Hz rTMS and an indirect relationship with ICF increase in depressed adolescents receiving 10 Hz rTMS.

Exploratory Aim 3

Aim 3a: To compare 7 T MRS cortical measures of GABAergic tone and glutamatergic neurochemistry in depressed adolescents and healthy control adolescents.

Aim3b: To examine potential changes in cortical GABAergic and glutamatergic neurochemistry after a six week course of either 1 Hz or 10 Hz rTMS in depressed adolescents.

Hypothesis:

1. Depressed adolescents will have decreased cortical levels of GABA as assessed with 7 T MRS compared to healthy control adolescents.
2. Depressed adolescents will have increased cortical levels of Glutamate as assessed with 7 T MRS compared to healthy control adolescents.
3. Bilateral cortical 7 T MRS measures of GABA will increase after 6 weeks of 1 Hz rTMS in depressed adolescents.
4. Bilateral cortical 7 T MRS measures of Gln/Glu will decrease after 6 weeks of 1 Hz rTMS in depressed adolescents.
5. Bilateral cortical 7 T MRS measures of GABA will decrease after 6 weeks of 10 Hz rTMS in depressed adolescents.

6. Bilateral cortical 7 T MRS measures of Gln/Glu will increase after 6 weeks of 10 Hz rTMS in depressed adolescents.

Exploratory Aim 4 examines clinical moderators of treatment (anhedonia and adversity) in this sample of adolescents undergoing treatment with 1 Hz and 10 Hz rTMS.

Hypothesis:

6 weeks of low frequency (1 Hz) rTMS vs. high frequency (10 Hz) rTMS will have greater efficacy (as assessed by CDRS-R) in depressed adolescents with anhedonia and adversity compared to depressed adolescents without anhedonia and adversity

The proposed project will examine an rTMS dosing, target engagement strategy for adolescent depression and refine understanding of GABAergic and glutamatergic contributions to negative valence. Findings will inform the clinical dissemination of rTMS for adolescent depression and provide insights to further treatment innovation for disorders of the negative valence systems domain early in life.^{9,52}

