3.2 Primary Study Endpoints

The primary study endpoint is depression severity (measured by CDRS-R total) over the 6-week study period.

3.3 Secondary Study Endpoints.

The secondary study endpoint is intracortical facilitation (ICF) over the 6-week study period.

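### Aim 2 prespecifies no 1 Hz versus 10 Hz contrast of ICF change, so a significant result in one arm only would be reported without the randomised test of frequency specificity

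*Combined protocol and SAP*

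**What the plan says.** Section 3.3 sets the endpoint: "The secondary study endpoint is intracortical facilitation (ICF) over the 6-week study period". Section 2 says that ICF "is the target engagement biomarker for the proposed trial". Section 2.2 states the predictions arm by arm: "We anticipate that ICF measures will decrease in depressed adolescents receiving 6 weeks of 1 Hz rTMS" and "We anticipate that ICF measures will increase in depressed adolescents receiving 6 weeks of 10 Hz rTMS".

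The analysis is in section 7.2, under Secondary Aim 2. Hypothesis 2a is tested in a model of the 1 Hz arm, and Hypothesis 2c "in a separate model, for those who receive 6 weeks of high frequency (10 Hz) rTMS treatment (Hypothesis 2c"). On contrasts it says: "LS mean contrasts (between ICF measurement time periods) from the mixed model will also be examined". The models relating ICF to CDRS-R (2b, 2d) are also read arm by arm. The Study Summary agrees: "a within-participant linear mixed model analysis of repeated measures will be used to examine the change in ICF over 6 weeks of rTMS".

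No section lists a treatment term, a treatment by time term or a 1 Hz versus 10 Hz contrast for ICF. The Aim 1 model for CDRS-R in the same section does include treatment as a fixed effect. Section 7.2 applies FDR adjustment where applicable and defines no family.

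**The concern.** The protocol says that every depressed participant receives active stimulation, with no sham. The healthy-control assessments listed in the notes to Table 3 include no TMS neurophysiology. The randomised comparison is therefore the only concurrent control for a time trend in ICF or for an effect common to both frequencies.

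Because the predictions point in opposite directions, any shared trend favours one hypothesis and works against the other. A downward trend helps 2a; an upward trend helps 2c. If one arm is significant and the other is not, the result looks like a frequency effect, but a difference in significance is not evidence of a difference in change.

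At stake is how the target engagement result is read. Section 5.3 matches the arms on intensity, duration, pulse number and site, so the between-arm contrast can show a frequency-specific change. It cannot show engagement as such.

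**Working it through.** **The plan's own figure.** Section 7.1 gives power for CDRS-R only: 25 per group, d = 0.61, six measures, correlation 0.50, two-sided 0.05. The SD of the mean of six measures is sqrt((1 + 5×0.5)/6) = 0.764. The SE of a two-group difference is 0.764×sqrt(2/25) = 0.216. Then 0.61/0.216 − 1.96 = 0.86, which is 80.6% power, as stated. No figure is given for ICF.

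**Inputs for ICF.** From section 7.1: 25 in each of four cells, so 50 evaluable per arm. Assumed: baseline-to-Week-6 correlation r = 0.5 (range 0.3 to 0.7), and a shared drift of 0.2 or 0.3 SD. Everything is in ICF SD units.

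**Standard errors at r = 0.5.**
- Within-arm change: sqrt(2(1−r)/50) = 0.141.
- Unadjusted between-arm difference in change: 0.141×sqrt(2) = 0.200.
- Baseline-adjusted between-arm difference: sqrt(2(1−r²)/50) = 0.173.

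**Shared drift, planned within-arm tests.**
- Drift 0.2: 0.2/0.141 − 1.96 = −0.55, so the predicted arm is significant in 29%. The other arm is not significant in about 71%. The product is 21%.
- Drift 0.3: 0.3/0.141 − 1.96 = 0.16, so 56%. The other arm is not significant in about 44%. The product is 25%.

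| Predicted arm significant, other arm not | drift 0.2 | drift 0.3 |
|---|---|---|
| Week 6 minus baseline, r = 0.5 | 21% | 25% |
| same, r = 0.3 | 17% | 25% |
| same, r = 0.7 | 25% | 17% |
| Overall 6-df time test, linear drift, r = 0.5 | 17% | 25% |
| FDR over 2a and 2c, r = 0.5 | 14% | 20% |
| FDR over 2a to 2d, 2b and 2d null and independent, r = 0.5 | 11% | 19% |

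The FDR rows come from 1,000,000 simulated trials per scenario.

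**Adding the contrast.** Under shared drift the true between-arm difference is zero. The share of trials with an arm significant as predicted and the between-arm contrast also significant in the predicted direction is 2.2% or 2.4% with the adjusted contrast, and about 2.3% to 2.5% with the unadjusted one.

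**Contrast power before FDR, r = 0.5.**
- Shifts −0.3/+0.3: adjusted 0.6/0.173 − 1.96 = 1.50, or 93%; unadjusted 0.6/0.200 − 1.96 = 1.04, or 85%.
- Shifts −0.3/+0.1: adjusted 64%.
- Shifts −0.3/0: adjusted 0.3/0.173 − 1.96 = −0.23, or 41%.

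By comparison, a planned within-arm test of a 0.3 SD shift has 56% power. With opposite 0.3 SD shifts, both within-arm tests succeed in only about 0.56² = 32% of trials.

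**When both arms succeed.** If 2a and 2c are each met at 1.96 in opposite directions, the unadjusted between-arm z is at least 3.92/1.414 = 2.77. The gap therefore concerns a result in one arm only.

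**The case against.** The plan tests what it predicts. Section 2.2 is worded as change within each arm, and its opening line, "Aim 2 examines changes in weekly ICF and CDRS-R across 6 weeks of either 1 Hz or 10 Hz rTMS", does not promise a comparison. No section says that one significant arm will be read as a frequency-specific effect. That stands: the plan contains no wrong inference to correct.

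A reader might infer that a one-arm result could never be separated from a shared change. The documents do not support this. The two models are fitted to independent randomised arms, and section 7.2 yields a change over time from each. Their difference and its SE follow directly, and even that unadjusted difference gives nearly the same protection. What is missing is prespecification, not information.

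A reader might also take the 29% or 56% as rates of false findings. If ICF truly falls in both arms, Hypothesis 2a is true, and these figures are the power to detect the assumed change. They become errors only under a claim about frequency that the plan does not make.

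The drift itself is assumed. ICF is not an entry criterion in sections 4.1 and 4.2 and both strata are enrolled, so selection on ICF gives no arm-level regression to the mean. With no drift, significance in the predicted direction is about 2.5% per arm before FDR.

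Finally, section 7.1 describes a proof-of-concept trial sized partly by resources, and ICF change does not drive the primary test.

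**Conclusion.** The gap is real but modest: Aim 2 has no prespecified between-arm ICF contrast, in a trial with no sham and opposite predictions for its target engagement biomarker. A one-arm result would be reported without the randomised test that separates a frequency-specific change from a common one.

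Under the assumed drift of 0.2 or 0.3 SD, r = 0.5 and 50 per arm, the easily misread pattern has a frequency of about 21% or 25% before FDR, and between 11% and 20% after FDR depending on drift and family. Neither FDR family can be called the planned one, because Aim 2 has four hypotheses and section 7.2 does not say which tests are adjusted together. The absence of the contrast does not depend on these assumptions; the size does.

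This should be changed, at the lower end of that grade: a secondary aim, an avoidable risk of misreading, and a cheap remedy.

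**What to change.** Keep 2a and 2c as within-arm changes. Add, as a prespecified Aim 2 test, the 1 Hz versus 10 Hz difference in ICF change at Week 6 from one longitudinal model of both arms. Either form works:

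- (a) Weeks 1 to 6 as responses, with baseline ICF by time, treatment, time and treatment by time. Take 2a and 2c from the planned per-arm models.
- (b) Baseline and Weeks 1 to 6 as responses, with baseline means constrained equal across arms. This is justified because section 4.3 completes baseline measurement before randomisation. Take 2a and 2c from this model.

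If ICF stratum is included, include stratum by time: the stratum is a cut of baseline ICF, so the gap between strata shrinks after baseline.

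Name the FDR family. State that a frequency-specific effect on ICF is claimed only if the between-arm contrast is significant, and that one significant arm alone is reported as within-arm change. Most of the protection comes from the contrast and this rule. The joint, baseline-adjusted model mainly adds precision (85% to 93% for −0.3/+0.3 before FDR).

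**Cost.** SAP text and one more test; ICF is already collected at baseline and weekly in both arms. With FDR over three tests (2a, 2c and the contrast), contrast power is about 88% for −0.3/+0.3 but about 32% if only one arm moves 0.3 SD. A real one-arm effect would then often be reported only as within-arm change. In that one-arm case, within-arm power goes from 46% (FDR over 2a and 2c) to 43% with the third test and per-arm models, or 48% with model (b), whose within-arm SE is sqrt((1−r²)/50 + (1−r)²/100) = 0.132 instead of 0.141. If the family is 2a to 2d, the starting point is about 36%.
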